6.10.3. Demographics

Age will also be summarized based on the following age categories 60-69 years, 70-79 years and above 80 years old.

6.11. Discontinuation of the study

On the 29th of March 2023 the EVERGREEN study was permanently terminated. All participants are to be followed up for 6 months post vaccinations for safety collection. ARIs will not be collected after the 29th of March 2023 or followed up.

Due to the early termination of the study, the Sponsor decided not to perform the complete planned analysis as described in the protocol and SAP. The final analysis will contain the following:

- Efficacy analysis for secondary endpoints and for a limited selection of the exploratory endpoints.
- Safety analysis presented only per period (as defined in [Table 4](#)).
- Immunogenicity analysis of all completed assays in the database at the time of the analysis.

Moreover, no local specific cohort analysis will be conducted.

The following efficacy endpoints will be analyzed per year and over the whole study:

- First occurrence of any RT-PCR-confirmed RSV-mediated LRTD and ARI
- First occurrence of any RT-PCR-confirmed RSV-mediated LRTD and ARI by subtype
- First occurrence of any clinically relevant diseases associated with RT-PCR-confirmed RSV-mediated LRTD and ARI
- AUC for participants with any RT-PCR-confirmed RSV-mediated LRTD and ARI
- Viral loads

Note: In the cases that an RSV ARI is ongoing during the time of the discontinuation and does not have an end date, the 29th of March 2023 will be used as an ARI end date. An ARI with no end date will be considered as an RSV ARI, if an RSV positive result is available within 15 days after the ARI onset.

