9.1. Statistical Hypotheses

The study is designed to test the primary hypothesis of VE against RT-PCR-confirmed RSV-mediated LRTD in the PPE population.

- The hypothesis for the primary endpoint is:

Null hypothesis: the VE against RT-PCR-confirmed RSV-mediated LRTD of Group 1 vs placebo is $\leq 20\%$.

Alternative hypothesis: the VE against RT-PCR-confirmed RSV-mediated LRTD of Group 1 vs placebo is $>20\%$.

Refer to Section 9.3 for the definition of the PPE population and to Section 9.4.1.1 for details on the primary endpoint. The analysis plan for the interim and primary analyses is provided in Section 9.5.1.

The study is successful if:

- The LL of the 95% 2-sided confidence interval (CI, potentially corrected as described in Section 9.4.1.3) around the VE (1-relative risk rate) calculated from the Exact Poisson regression model is above 20% and additionally a point-estimate of VE $>50\%$ is observed for Group 1

If VE for the primary endpoint is demonstrated, the following secondary endpoints will be tested:

1. First occurrence of any RT-PCR-confirmed RSV ARI, with onset at least 14 days after dosing of study vaccine
2. First occurrence of any RT-PCR-confirmed RSV-mediated LRTD during the second year, with onset after study Day 365
3. First occurrence of any RT-PCR-confirmed RSV ARI during the second year, with onset after study Day 365
4. First occurrence of predefined clinically relevant disease associated with RT-PCR-confirmed RSV-mediated ARI over the whole study, with onset at least 14 days after dosing of study vaccine

The following null and alternative hypothesis will be used for those secondary endpoints:

- The null hypothesis is that the VE for the considered secondary endpoint is $\leq 0\%$.
- The alternative hypothesis is that the VE for the considered secondary endpoint is $> 0\%$.

Formal inference for secondary endpoint #1, as part of the testing strategy, will occur at the time of the primary analysis. For secondary endpoints 2, 3, and 4, the formal inference as part of the testing strategy will only occur at study end. For more details on the secondary endpoints and the testing strategy, see Section 9.4.1.2 and Section 9.4.1.3.

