9.2. Sample Size Determination

9.2.1. Efficacy

The required sample size was determined using the following assumptions:

- a VE for RT-PCR-confirmed RSV-mediated LRTD of 65% during the first year and during the second year,
- an incidence of RT-PCR-confirmed RSV-mediated LRTD of at least 0.2% during the first RSV season (2021-2022) and an incidence of 0.5% in later RSV seasons in 60⁺-year-old placebo recipients,
- a randomization ratio of 2:1 (active vaccine: placebo),
- an analysis plan as described in Section 9.5.1
- a 1-sided α of 2.5% (potentially corrected for multiplicity), and
- 10% of exclusions (due to dropout, major protocol violations, etc.) per year

Simulations performed in R show that with ~15,340 participants in the active vaccine group (Group 1) and ~7,670 participants in the placebo group (Group 2) the study has at least 90% total power to demonstrate VE against the primary endpoint statistically significant $> 20\%$ and a point-estimate for VE $> 50\%$. This leads to a sample size of ~23,000 participants.

This sample size is also required to reach approximately 80% power for the secondary endpoint of first occurrence of RT-PCR-confirmed RSV-mediated LRTD during the second year.

Operating characteristics of the methods used with the sample size will be described in a separate modeling and simulations report.

In the proof-of-concept study (VAC18193RSV2001), which was performed in participants of at least 65 years of age, the observed VE for RSV-mediated LRTD (Case Definition 1) was 80% with corresponding 94.211% CI (52.2%; 92.2%). To account for uncertainty, a VE of 65% is used for the sample size determination. Further, an incidence of 1.1% for the primary endpoint selected for Phase 3 (Case Definition 1) was observed in study VAC18193RSV2001. The assumed incidence for the present study is decreased to 0.5% during the second RSV season to account for seasonal variability ([Belongia 2018](#)), and the potential impact of social distancing measures (anti-COVID) on the RSV incidence. As the impact of the anti-COVID measures on the first RSV season is unknown, the study covers for an incidence of RSV-mediated LRTD during the first RSV season of at least 0.2%.

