9.4.1. Efficacy Analysis

9.4.1.1. Primary Endpoint

The analysis of the primary endpoint will evaluate the first occurrence of RT-PCR-confirmed RSV-mediated LRTD (for the definition, see Section 8.2, Efficacy Assessments) with onset of at least 14 days after vaccination in the active vaccine group compared to the placebo group in the PPE population. Time at risk will also be taken into account. The null hypothesis of LL \leq 20% for RT-PCR-confirmed RSV-mediated LRTD will be tested versus the alternative hypothesis of LL $>$ 20%. Additionally, the observed VE should be $>$ 50%.

Exact Poisson regression will be fitted with the event rate, defined as the number of cases (with onset at least 14 days after vaccination) over the follow-up time (off-set) as dependent variable and the vaccination group, being at increased risk of RSV disease, and age stratum (both variables as stratified; see Section 6.3) as independent variables. Each participant will be taken into account in the model with one observation indicating whether they had a case or not, the vaccination group, the stratification factors, and the follow-up time.

The follow-up time is defined as the time between 14 days post-vaccination and occurrence of the first event. For non-cases, it is the time between 14 days post-vaccination and the database cut-off date of the analysis. However, for participants who discontinued or completed the study before that date and before having an event, follow-up time is defined as the time between 14 days post-vaccination and the date of last contact.

For participants with an MPD impacting efficacy during the second year, only the first year data are taken into account: for cases during the first year, the follow-up time is defined as the time between 14 days post-vaccination and occurrence of the first event. For non-cases, it is the time between 14 days post-vaccination and the Day 365 visit. Thus, all participants will be included in the analysis according to their follow-up time.

The study is 92successful if:

- The LL of the 95% 2-sided CI (potentially corrected as described in Section 9.4.1.3) around the VE (1-relative risk rate) calculated from the Exact Poisson regression model is above 20% and additionally a point-estimate of VE >50% is observed for Group 1

Sensitivity Analyses

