α_3	Alpha obtained from Pocock-like alpha spending function with information fractions = [# RSV LRTD events by 15 September 2022 / 76 [‡] , # RSV LRTD events by 24 October 2022 / 76 [‡] , # RSV LRTD events by 22 Jan 2023 / 76 [‡] , 1]
α_4	Alpha obtained from the remaining alpha to be spent (2.5% - total alpha spent during the interim analyses) and the actual information fractions observed at all analyses. That is, the information fraction, IF = [# RSV LRTD events by 15 September 2022 / # RSV LRTD events by 30 April 2023, # RSV LRTD events by 24 October 2022 / # RSV LRTD events by 30 April 2023, # RSV LRTD events by 22 January 2023 / # RSV LRTD events by 30 April 2023, 1]. The final alpha will be calculated using the user-defined alpha spending function approach (Jennison 2000).

[‡]76 target sample size for 90% power with 65% VE. Note that if at any of the interim analyses 76 or more RSV LRTD events have been observed, all remaining alpha will be spent and no further (interim) analyses for primary efficacy endpoint will be performed.

At the time of the primary analysis, unblinded safety and efficacy data will be analyzed. Immunogenicity data will be included if available.

Figure 3: Interim and Primary Analysis Plan

For the first interim analysis, ARIs with an onset up to 1 September 2022 will be included and a database cut-off of 15 September 2022 will be used. For the second IA, ARIs with an onset up to 10 October 2022 will be included and a database cut-off of 24 October 2022 will be used. For the third IA, ARIs with an onset up to 8 January 2023 will be included and a database cut-off of 22 January 2023 will be used. For the primary analysis, ARIs with an onset up to 15 April 2023 will be included and a database cut-off of 30 April 2023 will be used.

DB= database, IA= interim analysis, IDMC = independent data monitoring committee, PA=primary analysis, PPE=Per-protocol Efficacy, POS= positive

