6.3.3. Analysis Methods

The analysis of the primary endpoint will evaluate the first occurrence of RT-PCR-confirmed RSV-mediated LRTD with onset of at least 14 days after the vaccination in the active vaccine group compared to the placebo group in the PPE population. Time at risk will also be taken into account. The null hypothesis of LL \leq 20% for RT-PCR-confirmed RSV-mediated LRTD will be tested versus the alternative hypothesis of LL $>$ 20%. Additionally, the observed VE should be $>$ 50%.

Model:

Exact Poisson regression will be fitted with the event rate, defined as the number of events (with onset at least 14 days after vaccination) over the follow-up time (off-set) as dependent variable and the vaccination group, being at increased risk of RSV disease and age strata (both variables as stratified) as independent variables.

The model is defined with the *proc genmod* function in SAS, with an *offset* statement and a *log* (natural logarithm) link. The *exact* statement with the *estimate = both* option and an *alpha = 2**

significance level from Section 6.3.2 is used to calculate the relative risk ratio and its confidence interval. The Vaccine Efficacy is then calculated as $1 - \text{Relative Risk Rate}$.

In case the algorithm does not converge, age and risk level will be removed from the model.

Each participant will be taken into account in the model with one observation indicating whether they had an event or not, the vaccination group, the stratification factors and the follow up time.

Follow up time:

The follow-up time is defined as the time between 14 days post vaccination (vaccination day + 14 days) and occurrence of the first event; for participants with no events, it is the time between 14 days post vaccination and the minimum of the database cut-off date of the analysis. However, for participants who discontinued or completed the study before having an event, follow-up time is defined as the time between 14 days post vaccination and the date of last contact (day of discontinuation or completion).

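### Follow-up time for non-cases runs past the last date on which a case can count, which biases rates and time-to-event curves low but leaves vaccine efficacy essentially unchanged

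*SAP*

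**What the plan says.** SAP 6.11 was added when the study was terminated. It states that "ARIs will not be collected after the 29th of March 2023 or followed up", while all participants remain under safety follow-up until 6 months after vaccination. The one date it resets is the end date of an RSV ARI still open at termination, which becomes 29 March 2023. It gives no database cut-off for the final analysis and does not touch follow-up time.

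The follow-up rules are elsewhere:

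- **Cases** (SAP 6.3.3): the time between "14 days post vaccination (vaccination day + 14 days) and occurrence of the first event".
- **Non-cases still in the study** (Protocol 9.4.1.1): "it is the time between 14 days post-vaccination and the database cut-off date of the analysis". SAP 6.3.3 agrees.
- **Non-cases who discontinued or completed** (SAP 6.3.3): "follow-up time is defined as the time between 14 days post vaccination and the date of last contact", glossed as the day of discontinuation or completion.
- **Second year** (SAP 6.4.1.2.1): from the Day 365 visit to the earlier of the cut-off and completion or discontinuation.
- **Time to first occurrence** (SAP 6.6.1, Kaplan-Meier and Cox): the same clocks, with non-cases censored.

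Countable onsets close earlier. The notes to Protocol Figure 3, repeated in SAP 5.1, read: "For the primary analysis, ARIs with an onset up to 15 April 2023 will be included and a database cut-off of 30 April 2023". The three interim looks pair 1 with 15 September 2022, 10 with 24 October 2022, and 8 with 22 January 2023.

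**The concern.** Person-time belongs in a rate only while an event could have been observed and counted. Here the numerator stops at one date and the denominator at a later one, so unobserved days are treated as event-free days. Arm-level rates then come out too low. In a Kaplan-Meier or cumulative-hazard plot the extra days sit at the end of each non-case's clock. They inflate the late risk sets and flatten the tail of both curves, which is where a reader looks for durability.

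The SAP applies the right principle elsewhere. For participants with a second-year protocol deviation, later events are dropped and the clock stops the day before Day 365 (6.3.3). First-year analyses are capped in the same way (6.5.1). Only the end of case ascertainment has no matching rule.

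**Working it through.** **1. The plan's own figure.** Neither document gives a person-time rate to reproduce. The nearest design figure is 76 events for 90% power (note to Protocol Table 9). Inputs are "a 1-sided α of 2.5% (potentially corrected for multiplicity"), "a VE for RT-PCR-confirmed RSV-mediated LRTD of 65% during the first year and during the second year", 2:1 allocation, and the rule that the lower limit "calculated from the Exact Poisson regression model is above 20% and additionally a point-estimate of VE" exceeds 50%. Given the total number of events, the vaccine share is p0 = 1.6/2.6 = 0.615 at VE 20% and p1 = 0.7/1.7 = 0.412 at VE 65%. With exact boundaries, Pocock-like spending and several assumed four-look schedules ending at 76, power is 90.5% to 91.6%. The figure reproduces. It rests on how events split between arms, not on absolute rates.

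**2. Gaps between last countable onset and cut-off.** These are 14, 14 and 14 days at the interim looks and 15 days at the primary analysis.

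**3. Size of the understatement.** With d excess days and mean counted follow-up T, the rate is too low by d/T. For d = 14:

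| T (days) | 100 | 200 | 300 | 400 |
|---|---|---|---|---|
| Understated by | 14.0% | 7.0% | 4.7% | 3.5% |

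**4. Illustration by analysis.** Assumed, not in the documents: uniform enrolment over 300 days from about 1 August 2021, constant hazard, no dropout. Mean counted time is then days since 1 August 2021, minus 150, minus 14.

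- First interim: 410 − 164 = 246; 14/246 = 5.7%.
- Third interim: 539 − 164 = 375; 14/375 = 3.7%.
- Final analysis: true mean to 29 March 2023 is 605 − 164 = 441. If non-cases run to 30 April 2023 (+32 days), 32/473 = 6.8%. If to 31 May 2023 (+63 days), 63/504 = 12.5%. Both end dates are illustrative.
- Second year, mean at-risk time about 120 days: 32/152 = 21% and 63/183 = 34%, on the same illustrative dates.

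**5. Excess from the 6-month safety follow-up alone.** It arises only for people vaccinated after 28 September 2022, which is 182 days before 29 March 2023. If enrolment ended before then, it is 0%. If enrolment ran almost to 29 March 2023 (simulated as uniform over 600 days), the placebo rate falls from 5.071 to 4.654 per 1,000 person-years: 1 − 4.654/5.071 = 8.2%.

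**6. Curves and VE.** These come from a simulation of 3,000,000 participants with 0.5% per year in placebo, VE 65%, 2:1 allocation, and the enrolment pattern of step 4. Placebo cumulative hazard per 1,000 at the end of follow-up:

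| Analysis | SAP clock | Clock stopped at last countable onset | Too low by |
|---|---|---|---|
| First interim | 4.57 | 5.09 | 10% |
| Third interim | 6.41 | 6.95 | 8% |
| Final, +32 days | 7.17 | 8.14 | 12% |
| Final, +63 days | 6.54 | 7.91 | 17% |

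VE was 64.55% against 64.56% at the first interim look and moved by no more than 0.01 percentage points in any scenario. The reason is that excess time multiplies both denominators by nearly the same factor. The arms differ only because cases carry no excess, and cases are under 1% of either arm at the assumed incidences.

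**The case against.** The strongest reply is that no planned inference changes. The SAP reports VE with its confidence interval and proportions of participants with events. The proportions use no person-time, and the exact binomial sensitivity analysis ignores follow-up altogether. No efficacy output in either document is specified as events per person-year by arm. The curves of 6.6.1 are exploratory and are not named in the reduced list of 6.11. First-year analyses stop before Day 365, so participants past that day carry no excess there. The existing rule may also stop some clocks near 29 March 2023: last contact is glossed as the day of discontinuation or completion, and Protocol 7.2 lists a sponsor decision to stop the study as a withdrawal reason. Finally, SAP version 4.0 is dated 05/06/2023, after every interim and primary cut-off, so rewriting 6.3.3 for those looks would be retrospective.

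Most of this stands and limits the point to descriptive output. It does not remove it. The text does not say that 29 March 2023 ends efficacy follow-up, and for anyone still in safety follow-up it points to a later date. SAP 6.11 keeps the first-occurrence endpoints per year and over the whole study. Any rate or curve derived from them would be diluted unevenly, most in the second year. The timing objection governs how the four looks should be corrected, not whether the final analysis should be.

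**Conclusion.** The clock and the case window do not match, and the effect is confined to person-time rates and time-to-first-occurrence curves. The 14- or 15-day gap is fixed by the documents; its percentage effect depends on mean follow-up, which they do not give. The post-termination excess cannot be sized, because the final cut-off, last-contact dates and enrolment dates are absent. The 0% to 8% range for safety follow-up alone, and the larger figures for later cut-offs, are scenarios.

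A reader might infer more than the documents support:

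- **That VE or the success decision is compromised.** It is not, provided retention after 29 March 2023 is similar in both arms.
- **That counted time is several times the true at-risk time.** That could be so for an individual vaccinated shortly before termination, but no enrolment dates show how many such people exist, or whether any do.
- **That every planned analysis has the onset gap.** Onset windows are stated for four looks only, and not for the 31 January 2023, 31 May 2023 or end-of-study analyses.
- **That a case with onset on the first eligible day drops out through zero follow-up.** No day-count formula is given, and the per-protocol efficacy set already excludes RSV ARIs with onset within 14 days, which SAP 5.1 words inclusively for time since vaccination.

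**What to change.** In SAP 6.11, and by reference in 6.3.3, 6.4.1.2.1, 6.5.1 and 6.6.1, end efficacy follow-up for non-cases at the earliest of 29 March 2023, discontinuation or completion, and last contact. State the final-analysis cut-off date in the same place.

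For the three interim looks and the primary analysis, use the last countable onset date in place of the database cut-off. Where a look has already been run, report this as a correction or a sensitivity analysis beside the prespecified result.

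The cost is a date cap in the derivation of the follow-up variable and a rerun of the outputs that use it, plus a note wherever earlier results are shown for comparison. The hypothesis, alpha and case definition do not change. Membership of the per-protocol efficacy set should also stay as it is: requiring eligible time before the onset cut-off would redefine the analysis population, and this correction does not need it.

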8.1. ARI Assessments and Procedures

From study vaccination until 24 months after vaccination (ie, full duration of the study), participants will be followed up to identify potential cases of RSV infection (refer to [Appendix 7](#)).

After administration of study vaccine, ARI surveillance will be conducted for the duration of the study. To help participants remember to report symptoms of a possible ARI, ideally on the day of

symptom onset, written instructions are provided. A reminder will be sent to the participants twice every week until the end of the study, to remind participants to fill out the ARI surveillance question, which is always available, and to answer the question if they have experienced any ARI symptoms, or for participants who have one or more of these symptoms at baseline, if they have experienced any additional ARI symptoms or a worsening of their baseline symptoms. It is expected that the participants answer these questions at least twice a week, preferably on the days that the reminder is sent. Participants who experience any symptoms suggestive of an ARI are instructed to indicate this (refer to [Appendix 7](#)) and start completing the required ARI episode questionnaires on a daily basis (preferably in the evening) ([Appendix 8](#), [Appendix 9](#), and [Appendix 10](#)). Ideally within the next 24 hours, the site and participant should have telephone or telemedicine contact with each other in order for the site to confirm that the participant is experiencing symptoms consistent with an ARI^a and to give instructions to the participant on the ARI episode procedures to be followed (detailed in the subsequent section).

Figure 2: Schematic Overview of the ARI Assessments and Procedures

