5.2. Additional Analyses

Provided the primary efficacy analysis has occurred earlier, the following exploratory analyses might be performed depending on program needs:

1. **Exploratory analysis with database cut-off of 31 January 2023:** will include unblinded efficacy data, including secondary endpoints #2, #3 and #4. The latter will be considered an exploratory descriptive analysis. Formal inference of those endpoints as part of the testing strategy will only occur at study end. Safety data will be included when needed. Immunogenicity data will be included if available.
2. **Exploratory analysis with database cut-off of 31 May 2023:** will include unblinded efficacy data, including secondary endpoints #2, #3 and #4. The latter will be considered an exploratory descriptive analysis. Formal inference of those endpoints as part of the testing strategy will only occur at study end. Safety data will be included when needed. Immunogenicity data will be included if available.

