5.3. End-of-Study Analysis

The end of study analysis will include unblinded efficacy, safety and immunogenicity data. For secondary endpoints #2, #3 and #4, formal inference as part of the testing strategy will occur during this analysis.

Note: The timing of the end-of-study analysis is based on last subject last visit of the global cohort but will include all participants of global and local cohorts enrolled up to the cut-off of the final analysis.

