6.4.1.2. Level of Significance

The VE against the primary endpoint will be tested using the significance level α' (α_1 or α_2 or α_3 or α_4), as defined in Section 6.3.2. If the LL of the exact 2-sided CI ($1-2\times\alpha'$) for the VE (1-relative risk rate) calculated from the Exact Poisson regression model, is above 20% and the observed VE is above 50%, VE is demonstrated for the primary endpoint. If VE is demonstrated for the primary endpoint, the above secondary endpoints will be tested according to the testing order displayed in Table 10. The first secondary efficacy endpoint (first occurrence of any RT-PCR-confirmed RSV ARI) is tested using the same significance level α' as used for the primary endpoint. Exact 2-sided CIs ($1-2\times\alpha'$) for the VE (1-relative risk rate) will be calculated from these Exact Poisson regression models. If the LL of the CI is above 0%, VE will have been demonstrated for this endpoint and the next endpoint in the testing strategy can be tested. The following secondary endpoints (#2, #3 and #4) will be tested hierarchically at the end of the study at the full alpha ($\alpha=2.5\%$), as indicated in Table 10 below.

Table 10: Secondary Endpoints: Overview of the Testing Order, Timing of the Testing in the Testing Strategy and the Corresponding Alpha

Secondary endpoint: first occurrence of	Analysis timepoint in the testing strategy	Alpha at which the endpoint is tested
1. Any RT-PCR confirmed RSV ARI	Time of primary analysis	Alpha used at the primary analysis
2. Any RT-PCR confirmed RSV LRTD during the second Year	End of the study	2.5%
3. Any RT-PCR confirmed RSV ARI during the second Year	End of the study	2.5%
4. Predefined clinically relevant disease associated with RT-PCR-confirmed RSV-mediated ARI	End of the study	2.5%

Second year starts at the D365 visit

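### SAP 6.11 truncates the second year at 29 March 2023 but keeps the second-year and whole-study labels, leaves the inferential status of #2-#4 unstated, and does not end time at risk when case collection ends

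*SAP*

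**What the plan says.** SAP 6.11 records permanent termination on 29 March 2023. Safety follow-up continues to 6 months after vaccination, but "ARIs will not be collected after the 29th of March 2023 or followed up". It adds that "the Sponsor decided not to perform the complete planned analysis as described in the protocol and SAP". What remains, which 6.11 calls the final analysis, includes "Efficacy analysis for secondary endpoints and for a limited selection of the exploratory endpoints". It then says: "The following efficacy endpoints will be analyzed per year and over the whole study". The list covers RSV-mediated LRTD, RSV-mediated ARI and clinically relevant disease. Section 6.11 says nothing about alpha, hypothesis tests or the testing hierarchy.

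The testing text stands elsewhere in the SAP, without reference to the termination:

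- SAP 5.3 on the end-of-study analysis, which its note also calls the final analysis: "For secondary endpoints #2, #3 and #4, formal inference as part of the testing strategy will occur during this analysis".
- SAP 6.4.1.2: "The following secondary endpoints (#2, #3 and #4) will be tested hierarchically at the end of the study at the full alpha", with 2.5% for each in Table 10. This applies only if the primary endpoint and then #1 succeed.

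SAP Appendix 2, on changes to protocol-planned analyses, does not mention the termination. The planned surveillance is in Protocol 8.1: "From study vaccination until 24 months after vaccination (ie, full duration of the study), participants will be followed up to identify potential cases of RSV".

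**The concern.** Endpoints #2 and #3 ask whether protection lasts through a second year, and #4 covers the whole study. The design behind them is 24 months of surveillance per participant. Once case collection stops on a calendar date, each participant's second year is cut at a point set by the vaccination date, and late enrollees have none.

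A reader of a results table headed second year would take it to mean Day 365 to Month 24. If the gate is open, an analyst following the SAP as written would run the 2.5% tests on the truncated data and could report second-year efficacy as demonstrated. If the gate is closed, those tests are barred. Section 6.11 does not say which applies.

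Time at risk is a separate gap. Section 6.11 uses 29 March 2023 as the end date of ongoing RSV ARIs, but does not use it to close follow-up for participants without an event.

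**Working it through.** **1. Dates.** SAP 6.1.1 defines study day as date minus vaccination date plus 1. Month 24 is Day 730 with a window of -7/+14 days (Protocol 1.3.1), so Day 723 at the earliest.

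- Day 730 by 29 March 2023: vaccinated by that date minus 729 days = 30 March 2021.
- Day 723 by 29 March 2023: minus 722 days = 6 April 2021.
- Nominal Day 365 by 29 March 2023: minus 364 days = 30 March 2022. The SAP starts year 2 at the Month 12 visit, which may fall at Day 358. That moves this limit to 6 April 2022 at most.

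The anchors in the documents are Amendment 1 (3 May 2021), SAP v1.0 (6 July 2021) and a first RSV season of 2021-2022 (Protocol 9.2.1). Year-2 days = study day minus 364:

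| Vaccinated | Study day on 29 March 2023 | Year-2 days |
|---|---|---|
| 3 May 2021 | 696 | 332 |
| 6 July 2021 | 632 | 268 |
| 31 December 2021 | 454 | 90 |
| 30 March 2022 | 365 | 1 |

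Protocol 1.3.1, footnote b, provides for enrolment after 29 April 2022 (Northern Hemisphere) and after 14 October 2022 (Southern Hemisphere). Such participants contribute no year-2 time.

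**2. The plan's own figures.** Protocol 9.2.1 assumes VE 65%, placebo incidence 0.2% then 0.5%, 7,670 placebo participants, 2:1 allocation and 10% exclusions per year. Vaccine cases per placebo case = 2 × 0.35 = 0.7.

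- Both years: 7,670 × (0.90 × 0.002 + 0.81 × 0.005) × 1.7 = 76.3 events, against the stated target of 76.
- Year 2: placebo 7,670 × 0.81 × 0.005 = 31.1; active 15,340 × 0.81 × 0.005 × 0.35 = 21.7; total 52.8.
- Power for #2 (exact conditional binomial, Poisson event totals, one-sided 2.5%): 80.8% against a null of VE ≤20%, which matches the stated figure of about 80%, and 94.7% against VE ≤0%, the null given for the secondary endpoints.

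**3. Illustration: power.** The share of planned year-2 events captured is an assumption. Power for #2 against VE ≤0%:

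| Share captured | Expected events | Power |
|---|---|---|
| 100% | 52.8 | 94.7% |
| 75% | 39.6 | 87.0% |
| 50% | 26.4 | 70.1% |
| 25% | 13.2 | 37.8% |
| 10% | 5.3 | 12.8% |

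For scale, assumed uniform enrolment gives these mean shares of a 365-day second year before the stop: 47% (19 July to 31 December 2021), 29% (1 September 2021 to 31 March 2022) and 20% (19 July 2021 to 30 September 2022).

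**4. Illustration: waning.** Suppose VE falls linearly from 65% to 35% over year 2, with an even hazard. Average VE over the first fraction f is 65 - 15f. The full year gives 50%; f = 0.62 gives 56%; f = 0.31 gives 60%. The protocol itself assumes 65% in both years, in which case truncation causes no such bias.

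**5. Time at risk.** Non-case follow-up runs to cut-off, or to the date of last contact at discontinuation or completion (SAP 6.3.3). For year 2 it runs to the earlier of cut-off and completion or discontinuation (SAP 6.4.1.2.1). Section 6.11 gives no efficacy cut-off. Participants vaccinated after 29 September 2022 (29 March 2023 minus 181 days) reach Day 182 only after the stop, so they can add event-free time to whole-study analyses. For #2 and #3 the excess arises only where completion or discontinuation is dated after the stop. If person-time is inflated by the same factor k in both arms, the rate ratio (a/kT1)/(b/kT2) is unchanged. Absolute rates fall, and VE moves only if k differs between arms.

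**The case against.** The strongest defence is that the SAP never requires 24 completed months. Endpoints #2 and #3 are defined by onset after Day 365, second-year follow-up ends at cut-off, completion or discontinuation, and whole study means data up to cut-off. Participants who discontinue before Day 365 are already excluded from second-year analyses, and the exact Poisson model carries follow-up time as an offset. This stands as far as validity goes: the analysis estimates a coherent rate ratio for the window observed. It does not make the labels accurate.

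Three stronger readings are tempting, and the documents do not support them.

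- *Section 6.11 orders 2.5% tests on truncated data.* It names no alpha and says the complete plan is dropped. The fault is an unresolved conflict with 5.3, 6.4.1.2 and Table 10, and any test is conditional on the gate.
- *The stop inflates type I error.* SAP 5.2 allowed an "Exploratory analysis with database cut-off of 31 January 2023" that would include #2-#4, but only if the primary analysis had already occurred, and as exploratory and descriptive. Nothing says it took place or influenced the stop. Truncation with a person-time offset changes power and the part of year 2 seen, not the error rate.
- *It is a stated fact that nobody completed year 2.* It is a very strong inference from the dated anchors, but no first-vaccination date is given.

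**Conclusion.** The concern holds as an unresolved conflict and a labelling fault, not as an invalid test. The SAP version that added 6.11 aligned the start of year 2 but not its new end, and it did not reconcile the final analysis with the testing sections. Any second-year result describes the early part of year 2, with length varying by enrolment date.

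The size cannot be fixed from the documents. The date limits are firm arithmetic. The power, follow-up-share and waning figures are illustrations under assumed accrual, event capture and decline in VE. The direction is clear only if protection wanes, when the observed window would overstate full second-year VE. The person-time gap is real but probably small for VE, because it applies to both arms. The point deserves correction before the final analysis is reported. It does not by itself invalidate any result.

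**What to change.** Amend SAP 6.11, with cross-references to 5.3, 6.3.3, 6.4.1.2 and Table 10.

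1. End time at risk for all efficacy endpoints at 29 March 2023.
2. Label the periods Day 365 to 29 March 2023 and vaccination to 29 March 2023 (keeping the 14-day onset rule where it applies). Report by arm the number entering year 2 and the median and maximum year-2 follow-up.
3. State whether the primary endpoint and #1 succeeded, and whether #2-#4 are formally tested. If they are, limit the claim to the observed window and make no claim of full second-year or 24-month efficacy.

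The cost is a few sentences, a change to the follow-up derivation and one summary table. No new data are needed. Whether #2-#4 keep confirmatory status remains the sponsor's decision, but the SAP must state it.
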